2.5 Design of GUIDE-IT: Rationale for an Unblinded Study

GUIDE-IT will be an unblinded trial because blinding would eliminate one potentially important mechanism of treatment effect: the impact of patient knowledge of their own natriuretic peptide levels on adherence and health-related behaviors. Blinding GUIDE-IT would remove the patient from the critical role of active partnership in the management of his or her disease and would not reflect how biomarker-guided therapy will ultimately be used in practice, thus raising important issues about generalizability. We have taken multiple steps to minimize potential biases related to lack of blinding, including the use of an objective primary endpoint (cardiovascular death or HF hospitalization) and centralized adjudication of events by a Clinical Event Committee blinded to treatment assignment.

2.6 Design of GUIDE-IT: Rationale for Using NT-proBNP and Specific Target

Both BNP and NT-proBNP are widely clinically available and both markers have been used in previous trials of biomarker-guided therapy. We have selected NT-proBNP as the biomarker to be used for guiding therapy in the intervention arm of the GUIDE-IT study. The half-life of NT-proBNP is substantially longer than that of BNP (6 hours vs. 20 minutes), suggesting it is preferable for long-term therapeutic monitoring over time. For this reason, more prior studies have used NT-proBNP rather than BNP. NT-proBNP performed better in predicting long-term morbidity and mortality in a head-to-head comparison in Val-HeFT. Finally, the data supporting the validity of a specific natriuretic peptide target are stronger for NT-proBNP than for BNP.

Several lines of evidence have led us to select an absolute NT-proBNP target rather than a percentage change. First, the use of specific targets for physiologic parameters is standard in the management of other

cardiovascular diseases such a hypertension, hyperlipidemia, and diabetes. A strategy of targeting a specific percentage reduction may leave patients with elevated baseline values with a target that is still associated with substantial risk. The rationale for specific cut points is strongest if there is evidence for specific inflection points in the association of continuous physiologic parameters with risk. Data from the PRIDE study strongly suggests the presence of such a cut-off at approximately 972 pg/mL of NT-proBNP (Figure 4) 17 . Similarly, in an analysis of VAL-HeFT, the optimal cut point of NT-proBNP to define increased risk was 1078 pg/mL. Finally, as described above the interim results from the PROTECT pilot study demonstrated a strong signal for efficacy using an NT-proBNP target of 1000 pg/mL.³² The consistency of these findings around an NT-proBNP threshold of ~1000 pg/mL has led us to target that level of NT-proBNP suppression for GUIDE-IT.

2.7 Natriuretic Peptide Variability over Time

Understanding of intra-patient variability over time is of significant importance in using a biomarkerguided approach in order to distinguish between actionable change and normal biologic variation (i.e., to separate "signal" from "noise"). Araujo *et al* examined change in NT-proBNP levels over a period of 3 weeks in clinically stable, ambulatory HF patients without changes in therapy, and observed a high degree of intra-patient variability in subjects with low levels (<1000 pg/mL), but a more modest amount of variability in patients with levels in the HF range (~1000-10,000 pg/mL).⁴⁷ These data suggest that intrapatient variability is sufficiently limited to distinguish a clinical meaningful change from biological variability in chronic HF.

3. STUDY DESIGN

3.1 Overview

This study will be a multicenter, prospective, randomized, parallel control group, unblinded, 2-arm multicenter clinical trial comparing biomarker-guided therapy to usual care in patients with systolic HF at high risk for hospitalization or death.

3.2 Planned Number of Subjects and Centers

The planned enrollment for the GUIDE-IT study is approximately 1,100 subjects at approximately 40 centers in North America. To maximize generalizability, centers outside of North America may be considered for participation if HF management is sufficiently similar to U.S. practice and appropriate use of guideline-based therapy can be verified.

3.3 Study Duration

We anticipate the study duration will be 5 years: 6 months of start-up activities (i.e., finalize protocol, prepare study sites and contracts, receive site Institutional Review Board [IRB] approval), 36 months of active enrollment, 12 months of patient follow-up after the final patient is enrolled, and 6 months of study close-out, data analysis, and reporting of results.

4. STUDY POPULATION

4.1 Overview of Study population

The enrolled population will be high-risk patients with systolic HF (left ventricular ejection fraction [LVEF] \leq 40%). High-risk patients are defined below.

4.2 Inclusion Criteria

- Age \geq 18 years
- Most recent LVEF ≤ 40% by any method within 12 months of randomization
- High risk heart failure as defined by the following criteria
 - A Heart Failure Event in the prior 12 months, defined as any one of the following:
 - HF Hospitalization
 - Treatment in the Emergency Department (or equivalent) for Heart Failure
 - Outpatient treatment for heart failure with intravenous diuretics

AND

- NT-proBNP > 2000 pg/mL or BNP > 400 pg/mL at any time during the 30 days prior to randomization
- Willing to provide informed consent

4.3 Exclusion Criteria

- Acute coronary syndrome or cardiac revascularization procedure within 30 days (NOTE: Given that cardiac biomarkers such as troponin are frequently elevated in HF patients, the diagnosis of acute coronary syndrome should be based on clinical diagnosis, not biomarkers alone)
- Cardiac resynchronization therapy (CRT) within prior 3 months or current plan to implant CRT device
- Active myocarditis, Hypertrophic obstructive cardiomyopathy, pericarditis, or restrictive cardiomyopathy
- Severe stenotic valvular disease
- Anticipated heart transplantation or ventricular assist device within 12 months
- Chronic inotropic therapy
- Complex congenital heart disease
- End stage renal disease with renal replacement therapy
- Non cardiac terminal illness with expected survival less than 12 months
- Women who are pregnant or planning to become pregnant

- Inability to comply with planned study procedures
- Enrollment or planned enrollment in another clinical trial

5. STUDY INTERVENTIONS

GUIDE-IT will randomize patients in a 1:1 allocation to either:

- Biomarker-guided arm (approximately 550 subjects): Titration of HF therapy with a goal of achieving and maintaining a target NT-proBNP < 1000 pg/mL OR
- Usual care (approximately 550 subjects): Titration of HF therapy based on target doses from current evidence based guidelines

5.1 Biomarker-guided Arm

In the Biomarker-guided arm, NT-proBNP values from the local clinical laboratory will be utilized by treating physicians for the purpose of achieving at NT-proBNP target of < 1000 pg/mL. The GUIDE-IT protocol will specify interventions to be considered to achieve the NT-proBNP target in the biomarker-guided arm, but specific treatment decisions will be at the discretion of the treating physician. The order of implementation will be based on clinical judgment, and more than one intervention can occur in a single encounter. Titration of neurohormonal antagonists will be emphasized over titration of diuretics except in the case of clinically apparent congestion or in the case of very high NT-proBNP levels, which usually indicate subclinical volume overload. Specific changes in therapy and the rationale for them (e.g., in response to clinical change or NT-proBNP levels) will be captured on the eCRF. Potential interventions to decrease NT-proBNP levels will include:

- Up-titrate or add Angiotensin Converting Enzyme (ACE)-inhibitor or ARB
- Up-titrate or add beta-blocker (if not clinically congested)
- Up-titrate or add hydralazine-nitrates in African-American patients
- Increase loop diuretic dosage (if clinically congested or NT-proBNP > 5000 pg/mL)
- Up-titrate or add spironolactone if tolerated by renal function and potassium
- Add oral thiazide diuretic
- Add digoxin
- Consider adding ARB to ACE-I (if not on spironolactone)
- Consider hydralazine-nitrates in non-African-American patients
- Intensified or repeated heart failure education regarding diet, sodium restriction, etc.
- Consider optimization of cardiac resynchronization therapy (if CRT device implanted)
- Reconsider potential indications for CRT (if not previously implanted)
- If in atrial fibrillation, maximize rate control or consider more aggressive attempts at normal sinus rhythm
- Consider exercise training or cardiac rehabilitation

5.2 Usual Care Arm

Patients randomized to the usual care group will receive care based on the most recent AHA/ACC guidelines.⁴ Investigators will be provided with specific information on evidence-based target doses of neuro-hormonal antagonists (beta-blockers, ACE-inhibitors). Diuretics will be titrated based on clinical judgment of the treating physician. Routine assessment of natriuretic peptides **will not be performed** in the usual care group except for compelling medical reasons, consistent with current guidelines.⁴

6. STUDY PROCEDURES

A complete schedule of assessments throughout the study is given in Appendix A.

6.1 Screening

Clinical site staff will screen patients in both the inpatient and outpatient setting to identify high risk patients with systolic heart failure. If identified during a heart failure hospitalization, patients will not be randomized until the time of hospital discharge. A screening log will be maintained at each site. Eligible patients will provide written informed consent prior to randomization.

6.2 Randomization

Subjects who fulfill all the inclusion criteria and none of the exclusion criteria will be randomized in a 1:1 fashion using the Simple Internal Randomization Engine (SIRE) system to either biomarker-guided therapy or usual care. The unit of randomization will be at the patient level rather than the site level. Treatment allocation will be conducted using a complete randomization scheme. At randomization, subjects will undergo a brief interval history and physical exam, cardiovascular (CV) medication history, local laboratory testing for renal function and electrolytes, assessment for adverse events, 6 minute walk test, QOL questionnaires, medical resource use and cost assessment, and core laboratory samples.

6.3 Study Visits

6.3.1 Baseline

Baseline assessments will occur at the time of randomization and will include:

- Focused physical examination
- CV medication history
- Serum creatinine, blood urea nitrogen (BUN), and electrolytes (local laboratory)
- NT-proBNP (local laboratory)
- Health Related QOL questionnaire (as described in 6.7)
- 6 minute walk test
- Biomarker and DNA collection for biorepository (as described in 6.4)

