Rationale:	Current guidelines recommend that medical therapy be titrated toward the target doses used in clinical trials, but "therapeutic inertia" often represents a barrier to aggressive titration of medical therapy. There is a pressing need to develop strategies to improve utilization of proven therapies for HF in order to improve clinical outcomes and control costs. Observational studies have shown an association between decreasing natriuretic peptide levels over time and improved outcomes in patients with HF.
Objectives:	To compare a strategy of medical therapy titration aimed at achieving and maintaining an NT-proBNP target of < 1000 pg/mL (biomarker-guided therapy) to usual care in high risk patients with systolic heart failure.
Study Design:	Prospective, randomized, parallel controlled groups, unblinded, 2-arm, multicenter clinical trial of approximately 1100 patients.
Primary Endpoint:	Time to cardiovascular death or first HF hospitalization
Secondary Endpoints:	 Time to all-cause mortality Recurrent hospitalizations Days alive and not hospitalized for CV reasons Time to cardiovascular death Time to first HF hospitalization Health-related quality of life (HRQOL) Resource utilization, cost and cost effectiveness Safety

STUDY FLOW CHART

SCREENING

High risk systolic heart failure patients, with EF ≤ 40%, a heart failure event within prior 12 months, and NT-proBNP > 2000 pg/mL or BNP > 400 pg/mL during the 30 days prior to randomization

RANDOMIZATION

Randomized to either Usual Care (N=550) or Biomarker Guided NT-proBNP < 1000 pg/mL (N=550)

Baseline visit (day 0)

History and physical exam, CV medication history, serum creatinine, BUN and electrolytes and NT-proBNP (local lab), QOL questionnaire, medical resource use and cost assessment, 6MWT, biomarker and DNA sample collection

FOLLOW-UP

2-week follow-up (+ 1 week)

History and physical exam, CV medication history, change in HF therapy rationale, serum creatinine, BUN and electrolytes (local lab), NT-proBNP (local lab biomarker guided arm only), medical resource, cost assessment and biomarker samples

6-week follow-up (+ 1 week)

History and physical exam, CV medication history, change in HF therapy rationale, serum creatinine, BUN and electrolytes (local lab), NT-proBNP (local lab biomarker guided arm only), medical resource, cost assessment and biomarker samples

3-month follow-up (months 3, 6, 9, 12, 15, 18, 21, and 24) (+ 1 week)

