6.7 Quality of Life Assessments

GUIDE-IT will use a battery of validated instruments that build on a disease-specific core, supplemented by generic measures to provide a comprehensive assessment of health related QOL. These assessments of quality of life (QOL) will be performed at baseline by site coordinators and then 3 months, 6 months and annually to a maximum of 24 months by structured telephone interview conducted by the EQOL CC staff. A detailed description of each of these instruments with instructions will be included in the Manual of Operations. Assessments at each visit will include the following:

- Kansas City Cardiomyopathy Questionnaire (KCCQ)
- Duke Activity Status Index (DASI)
- enter for Epidemiological Studies Depression Scale (CES-D)
- Medical Outcomes Study Short Form (SF-12)
- Medical Outcomes Study Short Form (SF-36) subscales: General Health, psychological well-being, vitality, social functioning)
- EQ-5D

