7.3 Exploratory Endpoints

• Global Rank Endpoint, incorporating death, hospitalization, and change in quality of Life

• Win-ratio, incorporating death, hospitalization, and change in quality of life

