14. APPENDICES

14.1	Appendix A. Schedule of Study Assessments
------	---

	Screening	Day 0 (Randomization)	2 wks (+ 1 week)	6 wks (+ 1 week)	3 mos (+ 1 week)	6 mos (+ 1 week)	9 mos (+ 1 week)	12 mos* (+ 1 week)
Informed Consent	Х							
History and physical	Х	Х	Х	Х	Х	Х	Х	Х
CV Medication History	Х	Х	Х	Х	Х	Х	Х	Х
Document rationale for changes in therapy			Х	Х	Х	Х	Х	Х
6 minute walk		Х						
QOL**		Х			Х	Х		Х
Medical resource use and cost assessment		х	Х	Х	Х	Х	Х	Х
Local lab NT-proBNP (standard of care group)	х	х						
Local lab NT-proBNP (guided only)	Х	х	х	х	х	Х	X	Х
Cr, BUN, electrolytes (local lab)	Х	Х	Х	Х	Х	Х	Х	х
Core lab plasma sample		Х	Х	Х	Х	Х	Х	х
Core lab serum sample		Х	Х	х	Х	Х	х	х
Core lab DNA sample (once only)		Х						
Safety assessments			Х	Х	Х	Х	Х	Х
*Patients will be followe ** QOL will be administer					er QOL MOO.

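### The protocol does not require the baseline quality-of-life questionnaires to be completed before the arm is known, and the flow chart of this unblinded trial places the baseline visit after assignment.

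*Protocol*

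**What the plan says.** The synopsis describes the trial as "Prospective, randomized, parallel controlled groups, unblinded, 2-arm, multicenter clinical trial of approximately 1100 patients". Five places in the protocol bear on when baseline QOL is collected:

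- **Study Flow Chart.** The order is screening, then randomization to usual care or biomarker-guided therapy, then an entry beginning "Baseline visit (day 0" that includes the QOL questionnaire.
- **Section 6.2.** It describes allocation through SIRE and then continues "At randomization, subjects will undergo a brief interval history and physical exam", with the 6-minute walk and QOL questionnaires later in the same list.
- **Section 6.3.1.** "Baseline assessments will occur at the time of randomization and will include" the QOL questionnaire.
- **Section 6.7.** The QOL assessments "will be performed at baseline by site coordinators". Later ones are telephone interviews by the central EQOL staff. The battery is KCCQ, DASI, CES-D, SF-12, SF-36 subscales and EQ-5D.
- **Appendix A.** QOL is marked in the column headed "Day 0 (Randomization", with no mark under Screening.

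Health-related QOL is a secondary endpoint (section 7.2). Section 8.13 makes the KCCQ overall summary score and the DASI the primary QOL comparisons. Section 7.3 lists a global rank endpoint and "Win-ratio, incorporating death, hospitalization, and change in quality of life".

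**The concern.** A baseline is safe as a reference only if it cannot depend on the assigned arm. Blinding normally secures this. In an open trial the order of procedures has to do so, by collecting the baseline before the allocation is revealed. Self-reported health status is the kind of measure most open to a patient's hopes or disappointment about the arm, and the coordinator giving the questionnaire may know the arm too.

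If the two arms answer the baseline differently because they know their assignment, the difference passes into every contrast that uses baseline. Guided patients who report better at baseline would show too little improvement; if they report worse, they would show too much. Blinded event adjudication does not protect self-report, and central telephone interviews cover follow-up only. No later analysis can recover a clean baseline, so this is a matter for the protocol rather than the SAP.

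**Working it through.** **Step 1. What order do the passages fix?**

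| Place in protocol | Order relative to allocation |
|---|---|
| Section 6.1 | Consent must come before randomization; no baseline measure is mentioned |
| Study Flow Chart | Baseline visit listed after the split into arms |
| Section 6.2 | Allocation described first; assessments tied to randomization, order not fixed |
| Section 6.3.1 | At randomization, order not fixed |
| Section 6.7 | Coordinators administer at baseline; order not fixed, no masking stated |
| Appendix A | Single Day 0 column, order not fixed |

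The protocol fixes the order for consent but not for baseline QOL. The only place that shows a sequence puts baseline second.

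**Step 2. Which Day 0 items have an earlier measurement?** Appendix A marks history and physical, CV medication history, local NT-proBNP (the rows for both arms) and creatinine, BUN and electrolytes at Screening as well as Day 0. QOL and the 6-minute walk are marked at Day 0 only. The walk is never repeated and feeds no listed endpoint. That leaves QOL as the item that is self-reported, has no earlier value and is used in endpoints.

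**Step 3. Reproduce the plan's QOL power figure, to obtain the scale.** Inputs: 350 per arm, a difference of 0.25 SD, two-sided alpha 0.05 (section 8.6). In the normal approximation, power = Φ(0.25/√(2/350) − 1.96) = Φ(3.307 − 1.96) = Φ(1.347) = 91.1%, which agrees with the stated figure of more than 90%. With 550 per arm it is 98.6%. Section 8.13 equates 0.25 SD with about 5 KCCQ points, so SD ≈ 5/0.25 = 20.

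**Step 4. Illustrate the effect of a baseline shift.** Assumptions not in the protocol:
- a differential baseline shift d of 1 to 3 points that does not carry over to follow-up;
- a baseline-to-follow-up correlation ρ of 0.5 to 0.7;
- SD 20 at both times, 350 per arm and no true effect.

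Formulas:
- Change score: absolute bias = d; SD = 20√(2(1 − ρ)), which is 20.0 at ρ = 0.5 and 15.5 at ρ = 0.7.
- Baseline-adjusted: absolute bias = ρd; SD = 20√(1 − ρ²), which is 17.3 and 14.3.
- Standardized bias s = bias/(SD√(2/350)); two-sided type I error = 1 − Φ(1.96 − s) + Φ(−1.96 − s).

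For example, with d = 1 and ρ = 0.5, the change score has s = 1/(20 × 0.0756) = 0.66 and a type I error of 10.1%.

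| d | ρ | Change: bias | Change: type I error | Adjusted: bias | Adjusted: type I error |
|---|---|---|---|---|---|
| 1 | 0.5 | 1.0 | 10.1% | 0.5 | 6.7% |
| 1 | 0.7 | 1.0 | 13.7% | 0.7 | 9.9% |
| 2 | 0.5 | 2.0 | 26.3% | 1.0 | 11.9% |
| 2 | 0.7 | 2.0 | 40.1% | 1.4 | 25.4% |
| 3 | 0.5 | 3.0 | 51.0% | 1.5 | 20.9% |
| 3 | 0.7 | 3.0 | 72.6% | 2.1 | 49.4% |

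Against the 5-point benchmark the bias is 20% to 60% for change scores (1/5 to 3/5) and 10% to 42% with adjustment (0.5/5 to 2.1/5). With 550 per arm the bias is the same, but the type I error is higher because the standard error is smaller. A comparison of follow-up scores that ignores baseline has no bias from this source.

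**The case against.** Several counter-arguments have force.

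- **The text does not say after.** Sections 6.2 and 6.3.1 and Appendix A tie baseline to randomization without ordering the two. A reader might infer that the protocol mandates a post-allocation baseline. Only the flow-chart order points that way, so the supported statement is that the order is left open. This stands.
- **The sequence may be set elsewhere.** Section 6.7 leaves detailed instrument instructions to the Manual of Operations, which is not at hand. That is possible, but an unseen manual does not override a protocol flow chart that shows the opposite order.
- **The analysis may not use baseline.** Section 8.13 plans bootstrap treatment differences and mixed models and does not name change from baseline. This limits the reach of the point. Change in QOL is explicit only in the two exploratory endpoints, where section 8.12 lists QOL after death and hospitalization.
- **Section 2.5 is not evidence of a shift.** It concerns patients' knowledge of their own peptide levels and its effect on adherence and behaviour. It does not say that learning the arm changes answers the same day. This stands.
- **The size is assumed.** Step 4 shows what a shift would do. It does not show that one would occur.

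A reader might also infer that the primary analysis is at risk because baseline NT-proBNP is a Cox covariate (section 8.8). The documents do not support that. NT-proBNP is a laboratory assay, the core-laboratory measurement is central and blinded (section 6.4), and Appendix A also schedules a local value at Screening. Knowing the arm could alter the Day 0 value only if treatment changed before the draw. No passage schedules such a change, and Appendix A first marks the rationale for therapy changes at 2 weeks. Medication history likewise has a Screening record. Differential refusal of baseline questionnaires has no support either: section 8.13 expects refusal to be quite low.

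**Conclusion.** The point holds for the baseline QOL questionnaires. A site following the flow chart can collect them from a patient who already knows the arm, through a coordinator for whom no masking is stated, and there is no earlier measurement to fall back on. The analyses exposed are those of a secondary endpoint in so far as they use baseline, and the QOL component of the global rank and win ratio.

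The size cannot be derived from the document. The table gives the range under its stated assumptions, with a type I error from about 7% (1 point, adjusted) to about 73% (3 points, change score). The conclusion rests on the absence of any ordering requirement, not on those figures. It does not extend to the primary Cox analysis, to follow-up-only QOL comparisons or to any sample-size figure, and the 6-minute walk has no consequence for a listed endpoint. The correction is worth making because it closes the route at almost no cost.

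**What to change.** In sections 6.2 and 6.3.1, state that the baseline QOL questionnaires are completed before the site requests the allocation from SIRE. For consistency, apply the same rule to the other Day 0 baseline assessments and blood draws. In the flow chart, move the baseline visit above the randomization box. In Appendix A, divide the Day 0 column into a part before allocation and the allocation itself. Optionally, have SIRE release the arm only after the site confirms that the baseline forms are complete.

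The cost is protocol wording and, if the confirmation is adopted, one check in the randomization system. The assessments, the day and the sample size stay the same. The small downside is that a few patients may complete baseline and then not be randomized.
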